Prior studies did not use pedometers and also did not isolate the most vulnerable participants like frail older adults. Gillis et al.² studied 77 patients of varying physical status (i.e. all comers) scheduled in a randomized control trial. In this trial the authors compared a tri-modal intervention administered 4 weeks preoperatively and 8 weeks postoperatively for improving endurance, nutrition, and anxiety compared with a group that received this only postoperatively. At the end of the preoperative phase, patients receiving pre-habilitation walked on average 41.6m more during six minute walk distance (6MWD) testing than controls. However, the rate of postoperative complications did not differ significantly between groups and the cost and convenience of that intervention were unfavorable.

Dronkers et al.⁴ had both clinic-based and home-based exercise components in their preoperative intervention (with multiple trainers enlisted at presumed great cost). As part of their intervention they tracked patients with traditional pedometers. Despite these comprehensive efforts, they did not find any significant differences in endurance or clinical complications. One explanation for the lack of effect may be that the investigators did not use the pedometer for goal setting. Goal setting has proven itself when it comes to pedometers increasing physical activity / number of steps.¹⁰ In addition, neither the Dronkers nor Gillis study isolated frail older adults whose elevated baseline risk provides an increased opportunity for preventing adverse events.

Impact

We target frail older adults. Unlike prior prehabilitation studies, we focus on frail older adults. Working with this group provides a unique opportunity to make big gains in endurance and other aspects of physical status (relative to baseline status). In future work we can assess whether these relative gains translate into significant clinical outcome reduction.

Our intervention is low-cost and convenient. The convenience to patients of a home walking intervention will pay dividends in terms of adherence. Given the low baseline physical status of the patients we are recruiting, walking is the intervention that makes the most sense.

We are goal setting with a modern pedometer. Goal setting with a modern pedometer will

INVESTIGATOR STUDY PLAN - REQUIRED

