“After the first minute, tell the patient the following (in even tones): “You are doing well. You have 5 minutes to go.” When the timer shows 4 minutes remaining, tell the patient the following: “Keep up the good work. You have 4 minutes to go.” When the timer shows 3 minutes remaining, tell the patient the following: “You are doing well. You are halfway done.” When the timer shows 2 minutes remaining, tell the patient the following: “Keep up the good work. You have only 2 minutes left.” When the timer shows only 1 minute remaining, tell the patient: “You are doing well. You have only 1 minute to go.” Do not use other words of encouragement (or body language to speed up). If the patient stops walking during the test and needs a rest, say this: “You can lean against the wall if you would like; then continue walking whenever you feel able.” Do not stop the timer. If the patient stops before the 6 minutes are up and refuses to continue (or you decide that they should not continue), wheel the chair over for the patient to sit on, discontinue the walk, and note on the worksheet the distance, the time stopped, and the reason for stopping prematurely. When the timer is 15 seconds from completion, say this: “In a moment I’m going to tell you to stop. When I do, just stop right where you are and I will come to you.” When the timer rings (or buzzes), say this: “Stop!” Walk over to the patient. Consider taking the chair if they look exhausted. Mark the spot where they stopped.”

INVESTIGATOR STUDY PLAN - REQUIRED

Randomization: we will randomize patients in a 1:1 fashion into intervention and control groups using a prespecified table generated by our study statistician. More specifically we will use REDCap software to assign a study arm assignment using randomly permuted blocks of sizes 4 and 6.

Intervention patients: intervention patients will receive a walking prescription weekly calls from a study staff member as described below

Walking prescription: A study staff member in consultation with study physician (PI or co-I) will then provide the initial walking prescription based on the participants' baseline performance on the 6MWD following a published example^{12,13} and will focus the participant on walking at a moderate intensity (level of approximately 3 on the modified Borg Perceived Exertional Scale;¹⁴ laminated Borg scales will be distributed to participants).

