12. DATA AND SPECIMEN BANKING*

No specimens are being collected as part of the research. Data will not be banked for use in future research outside of the scope of this study.

13. Data Analysis and Management

Analysis As a first step, we will examine the distributions of all variables using histograms and summary statistics for continuous variables, and frequencies for categorical variables. We will consider transformations to enhance normality where continuous variables demonstrate substantial skew or outliers.

Aim 1: We will calculate the distribution of within-participant change for each of the five physical status measures and assess the average and median change against the minimal clinically important difference (MCID) for each assessment, as well as the percentage of patients with a minimal clinically important difference. In cases where a MCID is not available we will decide among our expert advisory team members the threshold values that indicate some important improvement. In our analysis we will also examine the role of baseline assessment on the amount of improvement by using a generalized linear model for the outcome of change in physical status controlling for baseline assessment.

Aim 1a: In this aim, we will examine the association of duration of time available for the intervention with within-participant change in physical status outcomes, using nonparametric locally-weighted scatterplot smoothing (LOESS) regression.¹⁷ We will rerun our generalized linear model controlling for duration of time available for the intervention, transforming the duration variable if indicated by the LOESS plots, e.g., piecewise linear if a threshold effect is seen.

Aim 1b: Similar to Aim 1a analyses, we will examine the association of percentage of days (of the 30 days available in pedometer memory), the step count target was met with within-participant change in physical status outcomes, again using LOESS plots. We will rerun our generalized linear model controlling for the percentage of days in which the patient met their step count target, transforming the percentage of days if indicated by the LOESS plots.

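### Section 13 reads the baseline coefficient in a change-on-baseline model as showing who improves more; with similar spread at both visits, that coefficient is expected to be negative even if walking does nothing

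*Combined protocol and SAP*

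**What the plan says.** Section 13 (Data Analysis and Management), Aim 1, first summarises "within-participant change for each of the five physical status measures" against the MCID. It then says the team will also "examine the role of baseline assessment on the amount of improvement by using a generalized linear model", and specifies a "generalized linear model for the outcome of change in physical status controlling for baseline assessment". No other term is named.

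The same model is carried forward. For Aim 1a: "We will rerun our generalized linear model controlling for duration of time available for the intervention". For Aim 1b: "We will rerun our generalized linear model controlling for the percentage of days in which the patient met their step count target". Neither rerun adds arm or an interaction with arm.

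A control group exists. Section 11 (Randomization) states that "we will randomize patients in a 1:1 fashion into intervention and control groups". The Aim 1 analysis text does not use it for this question, and the plan nowhere mentions regression to the mean or measurement error in the baseline value.

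**The concern.** Baseline is a sound covariate when the target is a difference between arms. Here the stated target is the baseline coefficient itself, read as the effect of starting level on improvement. Because change is follow-up minus baseline, any random error or day-to-day fluctuation in the baseline value enters the outcome with a minus sign and the predictor with a plus sign. This builds in a negative association. A patient who happened to do badly at the first visit tends to look improved at the second, and one who happened to do well tends to look worse.

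At stake is the answer to one Aim 1 question. The planned analysis can report that weaker patients benefit more from walking when nobody has benefited, and a larger sample makes that false finding more likely. A control arm that could separate the artefact from a real gradient is available but unused.

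**Working it through.** **Inputs.** From the documents: outcome, covariate and absence of an arm term (Section 13); 1:1 allocation (Section 11); 200 subjects (Section 24, and the Aim 2 paragraph of Section 13) or 400 (Sections 4 and 25). The plan states no SD, correlation, alpha or effect size for Aim 1, so there is no figure of its own to reproduce. Assumed: six-minute walk SD 100 m at both visits; rho 0.85, 0.90 or 0.95; two-sided 0.05; no true change.

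**Slope.** Slope = cov(follow-up − baseline, baseline) / var(baseline) = rho × (SD follow-up / SD baseline) − 1. With equal SDs this is rho − 1.

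**Apparent extra gain, one SD below versus one SD above the mean.** This is 2 × (1 − rho) × 100 m.

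**Chance that the false slope is significant.** With equal SDs, corr(change, baseline) = −√((1 − rho)/2). By Fisher's z, the chance is Φ(atanh|corr| × √(n − 3) − 1.96). For rho 0.90 and n = 200: atanh(0.224) = 0.2275; 0.2275 × √197 = 3.19; 3.19 − 1.96 = 1.23; Φ = 0.89.

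| rho | slope | apparent extra gain | corr | n = 100 | n = 200 |
|---|---|---|---|---|---|
| 0.85 | −0.15 | 30 m | −0.274 | 79% | 98% |
| 0.90 | −0.10 | 20 m | −0.224 | 61% | 89% |
| 0.95 | −0.05 | 10 m | −0.158 | 35% | 61% |

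The n = 100 column applies if the model is fitted in one arm of a 200-patient trial.

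**Check by simulation** (1,500 runs per setting, no effect of walking). At n = 200 the false slope was significant in 88% of runs for rho 0.90 and 63% for rho 0.95. At n = 400 the figures were 99.9% and 89%. With lower correlations of 0.7 and 0.8 it was significant in 100% and 99.6% at n = 200.

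**When the artefact disappears.** Setting rho × (SD ratio) − 1 = 0 gives an SD ratio of 1/rho: 1.18, 1.11 and 1.05 for rho 0.85, 0.90 and 0.95.

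**Does the control arm help?** Adding arm alone as a main effect leaves the slope in place. In the same no-effect simulations, an arm-by-baseline interaction averaged between −0.014 and 0.010 and was significant in 4.1% to 6.5% of runs, close to the nominal 5%.

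**Precision of the interaction.** SE per 100 m of baseline = 2 × 100 × √(1 − rho²)/√n. For rho 0.90 and n = 200: 200 × 0.436/14.14 = 6.2 m, so the 95% CI is about ±12 m per 100 m.

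**The case against.** The strongest reply is that this is a secondary sentence. The main Aim 1 outputs are average and median change against the MCID, and the interim rule in Section 13 uses those averages and medians. This mechanism does not touch them. That stands, and it limits the severity. A reader might infer that Aim 1 as a whole is invalidated; the documents do not support that on this point.

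A reader might also infer that the slope will be negative whatever the truth. It need not be. If fitter patients truly gain more, the spread widens, and at rho 0.90 a follow-up SD only 1.11 times the baseline SD brings the expected slope to zero. The artefact still pulls the estimate downward, so the coefficient remains uninterpretable as a benefit gradient.

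Two inferences about consequences go too far. One is that the slope would steer selection for the larger trial. Section 4 lists duration, step counts and adherence, recruitment time and cost, and satisfaction as information for that trial, not a baseline gradient. Entry to the walking study in Section 11 rests on the Edmonton score, not on baseline walk distance. The other is that the slope would falsely confirm the trial's rationale. Section 5 says "Working with this group provides a unique opportunity to make big gains in endurance", but that passage contrasts frail patients with the unselected patients of earlier trials and qualifies the gains as relative to baseline. It does not predict a gradient among those enrolled.

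Finally, the interaction is not a complete cure for bounded scores. Section 10 scores balance from 0 to 4, and a walking-arm patient already at 4 cannot show a benefit. A simulation with a rounded 0–4 score, n = 200 and a uniform latent gain of 0.5 points gave a mean interaction of −0.12, significant in 31% of runs, with 32% at ceiling at baseline. With 50% at ceiling it gave −0.18 and 56%. These inputs are assumed, but the direction is general. This objection stands and is met in the fix.

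**Conclusion.** The point holds. Section 13 states that the baseline coefficient will be read as the role of baseline in improvement, in a model where that coefficient is expected to be negative with no true change and similar spread at the two visits. No other section corrects this. The size depends on assumed values. For rho between 0.85 and 0.95 and an SD of 100 m, the spurious difference is 10 to 30 m between patients one SD either side of the mean, and a false significant slope is more likely than not at n = 200 (61% to 98%). It is likelier still at 400, so the conflict between the two stated sample sizes does not change the conclusion.

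The defect is confined to the interpretation of this coefficient, here and in the Aim 1a and 1b reruns. It is not an argument against adjusting for baseline. Severity: should fix.

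**What to change.** In Section 13, Aim 1:

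- Keep baseline as a covariate, and state that its coefficient will not be interpreted as showing who improves more.
- For each measure, add arm and an arm-by-baseline interaction. Randomization makes regression to the mean equal in expectation in the two arms, so it cancels in the interaction.
- Report the walking-minus-control difference in change, with 95% CI, at the 25th, 50th and 75th baseline percentiles, labelled exploratory.
- For bounded scores such as balance, state that a ceiling can by itself produce a negative interaction. Interpret the result with that caution, or report the share of patients at ceiling.

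The cost is a few sentences and two extra terms per measure, with no new data collection. The downside is imprecision: with an SE of about 6 m per 100 m of baseline (n = 200, rho 0.90), the result may well be inconclusive.

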4. OBJECTIVES*

Surgery is a life-saving procedure for patients with cancer and can enhance quality of life for patients with intractable abdominal or thoracic disease. Although most patients tolerate the procedure well, frail older adults have as much as a threefold increase in the risk of adverse outcomes after surgery.¹ In response to this risk, some investigators^{2,4} have studied preoperative exercise interventions (a.k.a. pre-habilitation).

So far, pre-habilitation studies^{2,4} have shown improvement in endurance but not a reduction in adverse outcomes such as medical complications, discharge to nursing home, or readmission. Potential explanations are that these studies were too small to show a difference but also they did not focus on frail older adults who could benefit most from prehabilitation. A final explanation is that they relied on clinic visits with physical therapists or kinesiologists which can add to the stress and cost of surgery for patients already burdened with appointments in the short preoperative period.

A home walking prescription self-monitored with a modern pedometer (e.g. Fitbit type wristband) provides a convenient and cost-effective method for prehabilitation. Despite the apparent advantages of a home walking program, no one has demonstrated that such a program can reduce the incidence of adverse outcomes or improve physical status assessments such as endurance, balance, gait speed, strength, and self-reported function. If our investigative group establishes that a walking prescription supported by pedometer improves these assessments, we would be in a favorable position to embark on a larger study to demonstrate a reduction in adverse clinical outcomes.

There are other data that would be helpful to collect prior to embarking on the larger study. These include the role of varying duration of the walking regimen. Given the rush to proceed with surgery in anxious patients, it would be important to know how well the intervention works over the range of times available and if there exists a threshold of duration (e.g. 1-2 weeks) below which a walking prescription would have no effect.

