Additionally, it would be important to analyze step counts from the pedometer and the percentage of days in which individual patients achieved prescribed targets. This would permit assessing whether any improvements in physical status resulted from the walking intervention. Conversely, if there is no improvement in physical status assessments, we could diagnose if nonadherence with the walking prescription was the reason. Finally, it would be helpful in guiding future research to calculate the time and cost required to recruit eligible patients as well as to assess patient satisfaction with the walking prescription.

INVESTIGATOR STUDY PLAN - REQUIRED

We therefore propose a study of 400 older adults scheduled for surgery with the following aims which will prepare us to conduct a larger trial focused on clinical outcomes.

Aim 1: To assess the impact of a walking prescription intervention on outcomes of endurance, balance, gait speed, strength, and self-reported function in patients with frailty.

Aim 1a: To estimate improvement in outcomes as a function of duration of the walking intervention.

Aim 1b: To re-estimate the effect of the intervention adjusting for the percentage of days each patient met his/her walking goal.

Aim 1c: To measure patient satisfaction with the walking intervention.

Aim 2: To measure the average time and cost required to recruit and follow up each patient.

Aim 3: Postoperative outcomes: we may also measure several postoperative outcomes

Change in six-minute walk distance from baseline

The number of steps per day in the hospital

Time to 100 steps at the day of discharge.

Discharge to skilled nursing facility

Length of stay

Thirty-day outcomes including serious complication, readmission, and death

Aim 4: Measure the performance of Edmonton frailty score for predicting 30 day outcomes including serious complication, readmission, death.

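### Aim 1a relates change to duration without regard to study arm, so it cannot show whether the effect of walking depends on the time available

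*Combined protocol and SAP*

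**What the plan says.** Section 4 (Objectives) gives the reason for the aim: "it would be important to know how well the intervention works over the range of times available". The same sentence then raises a second question, that of a minimum useful interval: "if there exists a threshold of duration (e.g. 1-2 weeks) below which a walking prescription would have no effect". The aim itself reads "To estimate improvement in outcomes as a function of duration of the walking intervention".

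Section 13 (Data Analysis and Management) gives Aim 1a two steps. The first is to "examine the association of duration of time available for the intervention with within-participant change in physical status outcomes", by LOESS. The second is "We will rerun our generalized linear model controlling for duration of time available for the intervention", with duration transformed if the curve suggests it, for example to a piecewise linear form when a threshold appears. The model being rerun is the one from Aim 1, a "generalized linear model for the outcome of change in physical status controlling for baseline assessment". Study arm is named in neither step, nor in that base model.

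Section 11 (Procedures Involved) states that "we will randomize patients in a 1:1 fashion into intervention and control groups". It puts the repeat walk test and SPPB usually three to five weeks after baseline and does not restrict them to one arm. How duration is to be measured is not defined.

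**The concern.** Whether a treatment works, and whether there is an interval below which it does not, are statements about walking compared with control. Asking how they change with time is a question of effect modification. The planned analysis instead describes how change from baseline varies with time.

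The two differ because duration is not assigned. It follows the surgical schedule, and section 4 itself mentions the pressure to operate quickly. Patients with more time may differ in diagnosis and urgency, and retest gains or natural recovery may also vary with the interval. Any such trend would appear in the controls as well, but the planned curve and coefficient never use the controls as a comparison. A shared trend could be read as a dose-response of walking, and a trend in the other direction could conceal a real one. Section 4 lists this among the information wanted before a larger study, so a misread curve could carry forward into that design.

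**Working it through.** **Nothing to reproduce.** The documents give no SD, alpha, power or target slope for Aim 1a. The figures below are illustrations, with assumptions marked.

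**Inputs**
- Allocation 1:1 (section 11).
- Usual interval 3 to 5 weeks (section 11). A uniform spread is assumed, so the SD of duration is 2/√12 = 0.577 weeks.
- Size of effect: 41.6 m on the walk test after a 4-week preoperative programme (the cited trimodal trial in section 5). Assuming linear growth from zero, this is 41.6/4 = 10.4 m/week.
- Shared trend of 5.2 m/week in either direction (assumed).
- N = 200 (sections 13 and 24) or 400 (sections 4, 10 and 25). The documents give both.
- SD of change 50 to 100 m and two-sided alpha 0.05 (assumed).

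**Step 1: what each model estimates.** Let D be duration and A be arm (1 = walking). Suppose change = a·A + g·(D − 4) + h·A·(D − 4) + error. Here g is the trend common to both arms and h is the growth of the walking effect per week. With 1:1 allocation and D unrelated to arm, the expected duration coefficients are:
- planned model (baseline and duration): g + h/2
- the same plus arm as a main effect: g + h/2
- walkers only: g + h
- arm-by-duration term: h

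Only the last is free of g.

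**Step 2: simulation check.** 2,000 trials of N = 400 with SD of change 70 m. Mean coefficients in m/week:

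| Truth | Planned | Plus arm | Walkers only | Arm-by-duration |
|---|---|---|---|---|
| Effect grows 10.4, no shared trend | 5.3 | 5.3 | 10.6 | 10.5 |
| Constant effect, shared trend 5.2 | 5.1 | 5.0 | 5.2 | 0.3 |
| Effect grows 10.4, shared trend −5.2 | 0.1 | 0.1 | 5.4 | 10.5 |
| No walking effect, shared trend 5.2 | 5.1 | 5.1 | 5.1 | 0.0 |

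The formula gives 5.2, 5.2, 0 and 5.2 for the planned model. The 0.3 in the last column is within simulation error: the standard error of the interaction is 12.1 m/week per trial, and 12.1/√2000 = 0.27.

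The planned coefficient is nearly the same in the first, second and fourth rows, which describe three different truths. In the third row it is close to zero although the walking effect does grow with time.

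**Step 3: precision of the right quantity.** SE of the slope difference = 2 × SD / (√N × SD of duration). The slope detectable with 80% power is (1.96 + 0.84) × SE.
- N = 200, SD 50 m: SE = 100/(14.14 × 0.577) = 12.2; detectable 34 m/week.
- N = 400, SD 50 m: SE = 100/(20 × 0.577) = 8.7; detectable 24 m/week.
- SD 100 m: 69 and 49 m/week respectively.

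Power for 10.4 m/week at SD 50 m is 14% at N = 200 and 23% at N = 400. If durations were spread evenly over 1 to 8 weeks (assumed), the detectable slopes at SD 50 m would fall to 9.8 and 6.9 m/week.

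**The case against.** The best defence is that the aim is worded as improvement as a function of duration. Improvement is within-participant change, and controls have no prescription whose duration could be measured. Read that way, section 13 matches the aim. It also has a tool for thresholds in the LOESS curve and the piecewise option. This reading fits the aim's sentence but not the question in section 4 that motivates it. The piecewise option changes the shape of the curve and adds no control comparison. Reading the plan as walkers only, or as having an arm term that was left unstated, does not help either (step 2).

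Two further objections stand in part. First, no model in section 13 names study arm, even for Aim 1, so this is partly a consequence of a wider omission. Adding arm to Aim 1 would still leave Aim 1a without its interaction. Second, an interaction does not make duration randomised. If urgent patients also respond less to walking, arm-by-duration will reflect case mix as well as time. That is a limit on interpreting the fix, and it has to be stated.

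A reader might also infer more than the documents support:
- *That duration is a post-randomisation variable.* Section 13 speaks of time available and does not define it. Section 24 has the surgical plan agreed before the patient is approached, so a scheduled interval could be known before allocation. The elapsed interval is known only afterwards. The fault is the missing definition.
- *That the programme could delay surgery unnoticed.* Nothing describes deferring surgery to allow walking. Section 11 keeps dates in the analytic dataset and uses the date of surgery for linkage. Only a tabulation by arm is missing.
- *That the plan has an inflated false-positive rate.* Aim 1a sets no significance test and is worded as estimation.

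**Conclusion.** The point holds as a mismatch between question and analysis. Section 4 asks how the effect of walking varies with time, while section 13 estimates how change varies with time, whatever the arm. With 1:1 allocation the planned coefficient equals the shared trend plus half the growth in effect, and the two parts cannot be separated. That result needs only linearity and duration unrelated to arm. The m/week figures rest on the assumed trend, SD and spread of durations.

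It should be corrected before analysis, but its weight is moderate: Aim 1a is a sub-aim of a preparatory study. The corrected analysis will also be weak. About 34 m/week (N = 200) or 24 m/week (N = 400) would be detectable at the most favourable SD considered, against an illustrative 10.4 m/week. Assuming a wider spread, with an SD of one week, would give about 20 m/week at N = 200 (2.8 × 100/14.14), but the usual interval in section 11 does not support that spread. Durations of 3 to 5 weeks also barely cover the 1 to 2 week threshold of interest. Low precision is a reason to call the result exploratory. It does not justify estimating a different quantity.

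**What to change.** In section 13, Aim 1a:
1. Draw the LOESS curves separately by arm.
2. Fit baseline, arm, duration and arm-by-duration, with duration piecewise if the curves suggest it. Report the walking-minus-control difference along duration with its 95% CI, labelled as exploratory estimation.
3. Define duration of time available, preferably as the interval to the preoperative or surgical date scheduled at randomisation, where one exists.
4. Tabulate the actual interval by arm from dates already held.
5. Adjust for surgery type (the principal procedure code is collected under section 10) and for indication where collected. State that any remaining variation of the effect with duration may reflect case mix, because duration is not randomised.
6. Reconcile the 200 and 400 sample sizes, since the expected precision depends on which applies.

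The cost is analysis-plan wording and, where a date is scheduled before allocation, recording it. No extra patients or visits are needed. The documents do not confirm that such a date always exists, so the definition needs a stated fallback. The price is a wide interval around the answer, which the plan should acknowledge in advance.
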